## 21.2 PRIMARY ENDPOINT

### PROPORTION OF EYES WITHIN 5 DEGREES OF ABSOLUTE IOL ROTATION

The primary endpoint for this study is the amount of absolute axis rotation from operative axis to the 1-week visit as measured by the photographic axis method. The proportion of eyes with less than or equal to 5 degrees of absolute rotation at 1-week will be reported along with the 95% confidence interval for this proportion.

The clinical success criterion will be that 90% of eyes will have lens rotation of 5 degrees or less at 1-week using the photographic measurement method.

The primary study endpoint is based on objective analysis of study photographs by designated sponsor personnel.

## 21.3 OTHER ENDPOINTS

### **Rotational Stability**

In addition to the absolute axis rotation at 1-week, data will also be reported at 1 day and 3 months. The proportion of eyes within 5° for all postoperative visits as well as the proportion of eyes with less than 10°, 20° and greater than 30° of rotation will be reported. Mean absolute rotation will also be reported for all visits using descriptive statistics.

### **Visual Acuity**

For visual acuity, the values will be converted to LogMAR prior to analysis. Descriptive statistics for all eyes will be reported for mean LogMAR monocular uncorrected and best corrected distance

visual acuity. The frequency and proportion of eyes achieving each acuity line will also be reported for uncorrected and best corrected distance visual acuity.

### **Residual Refraction**

Descriptive statistics will be reported for mean refractive cylinder, cylinder vs intended cylinder, spherical equivalent and spherical equivalent vs intended and for percent reduction in cylinder for all eyes. In addition, the frequency and proportion of eyes within 0.50 D and within 1.00 D of intended values will be reported for refractive cylinder and spherical equivalent.

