## **2. BACKGROUND/INTRODUCTION**

Approximately a third of patients presenting for cataract surgery are likely to have at least 1.0 D of corneal astigmatism. Patients with astigmatism that desire spectacle independence after cataract

---

surgery will need a method to eliminate or reduce corneal cylinder. Kessel et. Al., compared the two most commonly available options to reduce astigmatism and noted that the most effective way to reduce astigmatism is by implanting a toric IOL. For toric IOLs to be effective, IOL rotation after implantation must be minimal; it has been noted that as little as 1 degree of rotation can result in 3.3% reduction in the toric lens effectiveness in reducing astigmatism.

JJSV has developed a new IOL platform designed to minimize rotation to  $\leq 5^\circ$  within the first week after implantation. The TECNIS® Toric II 1-Piece lens is an ultraviolet light-absorbing posterior chamber intraocular lens (IOL) that compensates for corneal spherical aberrations and corneal astigmatism. The benefits of aspheric compensation for corneal spherical aberrations are contingent upon full refractive correction of sphere and cylinder. The IOLs incorporate a proprietary wavefront-designed toric aspheric optic with a squared posterior optic edge designed to provide a 360° barrier. The edge of the optic has a frosted design to reduce potential edge glare effects. In addition, compared to the TECNIS Toric 1-Piece IOL, the haptics of the TECNIS Toric II 1-Piece IOLs have a squared and frosted design. The anteriorly located cylinder axis marks denote the meridian with the lowest power and is to be aligned with the steep corneal meridian.

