### 6.2 OTHER ENDPOINTS

- Residual mean manifest cylinder and spherical equivalent for all eyes
- Percentage of eyes that achieve UCDVA of 20/40, 20/32, 20/25 & 20/20
- Percentage of eyes that achieve accuracy of cylinder (to target):
  - within:  $\pm 0.50$  D and  $\pm 1.00$  D
- Analysis of lens axis misalignment (compared to target) including:
  - Mean absolute and signed value of the misalignment
  - Percentage of eyes with lens axis misalignments  $\leq 5^\circ$ ,  $< 10^\circ$ ,  $< 20^\circ$  and  $>30^\circ$
- Medical findings/Lens findings/Complications
- Subject responses on Patient Satisfaction Questionnaire (PSQ)

**NOTE:** Should be administered only in subjects who have been implanted with the study lens bilaterally

- Investigator responses on Investigator Satisfaction Questionnaire (ISQ)
- Adverse event rates including the rate of IOL repositioning and/or IOL exchange primarily due to IOL misalignment.

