**TABLE 1: TECNIS® Toric II Models ZCU, IOL Astigmatism Correction Range**

	Cylinder Powers (D)						
IOL Model	ZCU150	ZCU225	ZCU300	ZCU375	ZCU450	ZCU525	ZCU600
IOL Plane (Labeled)	1.50	2.25	3.00	3.75	4.50	5.25	6.00
Corneal Plane*	1.03	1.54	2.06	2.57	3.08	3.60	4.11

\*The corresponding cylinder values at the corneal plane have been calculated based on the average pseudophakic eye.

**Table 2** lists the general design characteristics of the TECNIS Toric II IOLs.

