### 8.1 INCLUSION CRITERIA

1. Minimum 22 years of age;
2. Unilateral or Bilateral cataracts for which cataract extraction and posterior chamber IOL implantation have been planned;
3. Pre-existing corneal astigmatism of one diopter or greater;
4. Predicted residual refractive cylinder based on toric IOL calculator, considering surgically induced astigmatism (SIA) and posterior corneal astigmatism (PCA) must be  $\leq 0.50$  D;
5. Potential for postoperative BCDVA of 20/30 Snellen or better;
6. Clear intraocular media other than cataract in each eye;
7. Availability, willingness and sufficient cognitive awareness to comply with examination procedures and study visits;
8. Signed informed consent form (ICF) and health insurance portability and accountability act (HIPAA) authorization;
9. Ability to understand and respond to a questionnaire in English.

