**10.5 SELECTION OF THE IOL**

In order to facilitate IOL selection and axis placement, JJSV provides a web-based proprietary tool, the TECNIS Toric Calculator ([www.TecnisToricCalc.com](http://www.TecnisToricCalc.com)) for the surgeon. Preoperative keratometry, biometry data, incision location, spherical equivalent IOL power, and the surgeon's estimated surgically induced corneal astigmatism are used as inputs for the TECNIS Toric Calculator. These inputs are used to determine the axis of placement in the eye and the predicted residual refractive astigmatism for TECNIS Toric II 1-Piece IOL models.

**NOTE:** *The TECNIS Toric Calculator also provides an option for including the Posterior Corneal Astigmatism (PCA). The predetermined value for posterior corneal astigmatism must be included in the calculation by checking the box labeled "Include Posterior Corneal Astigmatism (PCA)".*

*Surgeons can use their preferred Toric Calculator for determination of lens axis placement.*

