### ADDITIONAL OPERATIVE INFORMATION COLLECTED SHOULD INCLUDE:

- Date of surgery
- Operative eye
- Lens power and serial number
- Intended spherical equivalent
- Intended cylinder
- Capsular bag polishing
- Lens placement
- Surgical complications or other surgical procedures
- Difficulty of lens implantation
- Product complaints
- Serious and/or device-related adverse events
- Confirmation that surgical photos have been taken/uploaded

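### Cylinder accuracy to target is scored in dioptres with no axis term, so the 0.50 D band can look better than the vector prediction error and registers lens rotation only at a larger angle

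*Combined protocol and SAP*

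**What the plan says.** Section 6.2 lists, among the other endpoints, "Percentage of eyes that achieve accuracy of cylinder (to target"), with bands of plus or minus 0.50 D and 1.00 D. Section 21.3 (Residual Refraction) repeats the rule as "eyes within 0.50 D and within 1.00 D of intended values will be reported for refractive cylinder", and the Synopsis (Data Analysis) agrees. The remaining cylinder summaries have no axis either: "Descriptive statistics will be reported for mean refractive cylinder, cylinder vs intended cylinder, spherical equivalent" and percent reduction in cylinder.

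The target is not defined. The nearest definition is inclusion criterion 4 in section 8.1: "Predicted residual refractive cylinder based on toric IOL calculator, considering surgically induced astigmatism (SIA) and posterior corneal astigmatism (PCA) must be" at most 0.50 D. Section 10.5 says the sponsor's calculator is used to "determine the axis of placement in the eye and the predicted residual refractive astigmatism", although surgeons may use another calculator. The operative data list in section 10.6 has "Intended cylinder" and names no axis for it. On the achieved side, Appendix F refines both axis and power in the manifest refraction.

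**The concern.** Astigmatism has a magnitude and an axis. Two eyes with the same residual magnitude can be different distances from the plan. A plus/minus band in dioptres fits a plain difference of magnitudes, because the length of a vector difference cannot be negative. A difference of magnitudes never exceeds the vector difference, so any discrepancy between the two rules runs in the favourable direction.

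Criterion 4 removes half of the band. With a target of at most 0.50 D, the lower limit (target minus 0.50 D) is never above zero, and achieved magnitude cannot be negative. Only the upper limit can fail an eye.

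At stake is how the reported share is read. A reader may take it as the accuracy with which the planned astigmatic result was reached, when it shows only that little more astigmatism was left than planned.

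**Working it through.** **Inputs.** Lens cylinder at the corneal plane, C, is from Table 1: "Corneal Plane* 1.03 1.54 2.06 2.57 3.08 3.60 4.11" for ZCU150 to ZCU600. The target residual r runs from 0 to 0.50 D (criterion 4, taken as the intended cylinder). Section 21.5 expects 95% or more of eyes within 5 degrees; section 21.2 sets success at 90%.

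**The plan's own figures.** No figure is given for cylinder accuracy. The sample-size statement reproduces: 1.96 × √(0.95 × 0.05 / 200) = 3.02%, against the stated 3.0%. Section 2 says "as little as 1 degree of rotation can result in 3.3% reduction in the toric lens effectiveness". The model below gives 2 sin(1°) = 3.5% of C per degree, close to that.

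**Step 1: model.** Take a lens aligned with the steep meridian and otherwise exactly on plan, with corneal cylinder K = C + r (under-corrected) or K = C − r (over-corrected). After rotation by t, in double-angle terms:

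- residual magnitude = √(r² + 4KC sin²t)
- vector error = 2C sin t

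**Step 2: limits for 0.50 D.** The vector rule fails when sin t > 0.50/(2C). The magnitude rule fails when the residual exceeds r + 0.50. Since (r + 0.50)² − r² = r + 0.25, this means sin²t > (r + 0.25)/(4KC). At r = 0, K = C and the two limits are identical.

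Largest rotation, in degrees, that still counts as within 0.50 D:

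| Model | C (D) | Vector, any target | Magnitude, r = 0.25, under | Magnitude, r = 0.50, under | Magnitude, r = 0.50, over |
|---|---|---|---|---|---|
| ZCU150 | 1.03 | 14.0 | 17.9 | 20.2 | 35.9 |
| ZCU225 | 1.54 | 9.3 | 12.3 | 14.1 | 20.0 |
| ZCU300 | 2.06 | 7.0 | 9.3 | 10.9 | 14.0 |
| ZCU375 | 2.57 | 5.6 | 7.5 | 8.9 | 10.8 |
| ZCU450 | 3.08 | 4.7 | 6.3 | 7.5 | 8.8 |
| ZCU525 | 3.60 | 4.0 | 5.4 | 6.5 | 7.4 |
| ZCU600 | 4.11 | 3.5 | 4.8 | 5.7 | 6.5 |

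A target at an oblique axis can widen the magnitude limit further (up to 21.3 degrees for ZCU300 at r = 0.50).

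**Step 3: one eye.** ZCU300, r = 0.50 D under-corrected, rotated 10 degrees: residual = √(0.25 + 4 × 2.56 × 2.06 × 0.0302) = 0.94 D, with its axis 24 degrees off plan. The magnitude difference is 0.44 D, which passes. The vector error is 2 × 2.06 × 0.1736 = 0.72 D, which does not.

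**Step 4: how many eyes, from rotation alone.** Assume rotation is normal with mean 0, and targets uniform on 0 to 0.50 D; neither is in the documents. With 95% within 5 degrees, the SD is 5/1.96 = 2.55 degrees. For ZCU600 the vector rule passes P(|Z| ≤ 3.49/2.55) = 82.8%. The magnitude rule, averaged over under-corrected targets, passes 92.8%. The gap is about 10%. For ZCU450 the shares are 93.2% and 98.0%, a gap of about 5%. For ZCU300 the gap is 0.5 to 0.6%, and for ZCU150 about 0%. With only 90% within 5 degrees (SD 5/1.645 = 3.04), the gaps are just under 2% (ZCU300), 8 to 9% (ZCU450) and 12 to 14% (ZCU600), from under- to over-corrected.

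**Step 5: the 1.00 D band.** At r = 0.50 under-corrected, the magnitude and vector limits are 34.3 and 29.0 degrees for ZCU150, and 9.3 and 7.0 for ZCU600. Few eyes reach these: under Step 4's 95% case the gap is at most about 0.5%, for ZCU600.

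**Step 6: total error, illustrative only.** Suppose the vector error from all sources is bivariate normal with SD 0.25 to 0.30 D per component, again with uniform targets. Then 94.6% to 88.5% of eyes pass 0.50 D by magnitude, against 86.5% to 75.1% by vector. The SDs are assumptions, and this error would also include refraction, keratometry and surgically induced astigmatism. It is not a rotation effect.

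**The case against.** The strongest reply is that rotation is measured directly. The primary endpoint is photographic rotation, and sections 6.2 and 21.3 add misalignment summaries and cut-points at each visit. A rotated eye is counted there whatever its cylinder score. This largely stands, with one gap: the 5-degree cut is the same for every lens power, while the dioptric effect grows with power. A ZCU600 eye rotated exactly 5 degrees meets the primary criterion. At a 0.50 D under-corrected target it also passes the magnitude rule (difference 0.41 D), yet its vector error is 2 × 4.11 × sin 5° = 0.72 D.

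Other replies stand as limits:

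- Magnitude-only scoring is read from the plus/minus bands and the absence of any axis term; the plan does not say it outright.
- Reading the intended cylinder as the predicted residual is an inference. If the target is 0 D for every eye, the rules agree and only the missing definition remains.
- The case report form is not in the documents, and Appendix A lists a targeted refraction preoperatively. That no intended axis is recorded is therefore not established.
- Ending with less astigmatism than predicted is not a worse outcome, and no eye above 1.00 D residual can pass the 0.50 D band. The magnitude result has its own use.
- From rotation alone, the gap matters only for the higher-power models, and the documents give no expected model mix.

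A reader might go further and infer that the rule misses rotation error. It does not: rotating an aligned lens always raises the residual above target, so the rule detects rotation, but later. For the same reason rotation cannot turn a planned 0.50 D at one axis into 0.50 D at the perpendicular axis with zero scored error; that would need a wrong amount of correction. Nor do the documents say that this endpoint is there to demonstrate the effect of rotational stability.

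**Conclusion.** The point holds as a modest improvement to a secondary summary. As written, the 0.50 D band gives a result at least as favourable as the vector prediction error and tolerates more rotation: roughly 1.4 to 1.6 times the vector limit at a 0.50 D under-corrected target (20.2/14.0 = 1.4 for ZCU150; 5.7/3.5 = 1.6 for ZCU600). The difference shrinks to nothing as the target approaches 0 D, and it is negligible in the 1.00 D band.

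The angle limits rest on Table 1, an aligned and otherwise on-plan lens, and the reading of the intended cylinder as criterion 4's predicted residual. The shares of eyes also rest on assumed rotation and target distributions.

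A reader might infer that the trial's main conclusion is at risk. The documents do not support that: cylinder accuracy has no success criterion or test, and the primary endpoint does not use it.

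**What to change.** In the Synopsis, section 6.2 and section 21.3, define the intended cylinder as the predicted residual refractive cylinder, magnitude and axis, from the toric calculation used for that eye. Convert intended and achieved cylinder to double-angle components at one stated plane. Report the proportions of eyes with vector error at most 0.50 D and at most 1.00 D, next to the existing magnitude result. Add the intended axis to the operative data list in section 10.6 if the form does not already hold it. The achieved axis is already obtained in the manifest refraction.

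The cost is one case report form field and a few lines of analysis code, with no new tests, visits or subjects. The share within 0.50 D by vector will probably be somewhat less favourable than the share by magnitude, and it cannot be more favourable.

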### **Adverse Events**

The frequency and proportion of eyes with medical/lens findings or adverse events will also be reported.

### **Other Findings**

Enrollment data, demographic data, accountability data and operative complications/ procedures will be reported using descriptive statistics.

### **Patient Satisfaction and Investigator Satisfaction Questionnaires**

For questionnaires, the frequency and proportion with each response will be reported for the individual items on the questionnaire.

## **21.4 INTERIM REPORTS**

Multiple interim study analyses may be conducted during the study.

## **21.5 SAMPLE SIZE CALCULATIONS**

With 200 eyes, the two-sided 95% confidence interval for the proportion of eyes within 5 degrees of absolute rotation at 1-week will extend within 3.0% from the observed proportion assuming an expected proportion of 95% or higher.

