**STUDY POPULATION CHARACTERISTICS:**

**Condition:** Unilateral or bilateral cataracts with corneal astigmatism of approximately 1.0 D to 6.0 D.

Models ZCU 1.50, 2.25, 3.00, 3.75, 4.50, 5.25, 6.00

**Number of Subjects:** Up to 192 subjects will be enrolled to achieve 200 evaluable eyes at the 1-week visit with a target of 75% of the eyes coming from bilateral subjects and 25% of the eyes coming from unilateral subjects.

Each site should enroll approximately 24 subjects and no site may enroll more than 25% of the enrollment total.

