## 8. STUDY POPULATION

All study subjects will be enrolled from the normal surgical cataract population at up to 8 sites in the U.S. Up to 192 subjects (116 bilateral and 76 unilateral) will be enrolled to achieve approximately 200 eyes available for analysis at 1-week with a target of 75% of the eyes coming from bilateral subjects and 25% of the eyes coming from unilateral subjects. This accounts for screen failures, drop-out rate and unanalyzable photographs for toric IOL rotation analysis. Each site should implant approximately 24 subjects and no site may implant more than 25% of the enrollment total.

This study will include subjects undergoing unilateral and bilateral primary cataract extraction and IOL implantation and who meet all the study inclusion and exclusion criteria in one or both eyes. Subjects who meet the eligibility criteria will be offered enrollment in the study. Eligibility criteria may not be waived by the investigator. Any questions regarding patient eligibility are to be discussed with JJSV prior to subject enrollment. Those subjects who meet the eligibility criteria and agree to participate will receive the TECNIS Toric II IOL Model ZCU in one or both eyes.

Subjects will be enrolled at each site sequentially until the overall study recruitment goals are met or the site limit is reached.

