### **21.1 ANALYSIS POPULATION**

For monocular endpoints, all eyes implanted with a study toric IOL (model ZCU150 through ZCU600) will be pooled together for analysis; which include both study eyes from bilaterally implanted subjects and one study eye from unilaterally implanted subjects. For binocular endpoints (i.e., binocular visual acuity and patient satisfaction questionnaire), only bilaterally

implanted subjects will be included for analysis. Available data will be used for analysis (i.e., no data imputation for missing data).

For the rotational stability endpoint, the primary analysis population will be all eyes implanted with a study toric IOL (model ZCU150 through ZCU600) and with available valid axis data at the 1-week visit.

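### The 3.0-point precision in section 21.5 assumes 200 independent eyes, but about three quarters are to come in pairs and section 21 makes no allowance for fellow-eye correlation

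*Combined protocol and SAP*

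**What the plan says.** Section 21.5 gives one reason for 200 eyes, which is precision. The two-sided 95% interval for the primary endpoint "will extend within 3.0% from the observed proportion assuming an expected proportion of 95% or higher". It names no interval method and no correlation.

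The eyes are not all from different people. The Synopsis sets the evaluable target and how much of it bilateral subjects should supply: "Up to 192 subjects will be enrolled to achieve 200 evaluable eyes at the 1-week visit with a target of 75% of the eyes". Section 8 gives the enrolment ceiling by type of subject: "Up to 192 subjects (116 bilateral and 76 unilateral) will be enrolled to achieve approximately 200 eyes available for analysis at 1-week". The intended mix, which section 10.1 repeats, is stated in section 8 as well: "with a target of 75% of the eyes coming from bilateral subjects and 25% of the eyes coming from unilateral subjects". Section 8 then explains what the enrolment margin is for: "This accounts for screen failures, drop-out rate and unanalyzable photographs for toric IOL rotation analysis".

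Section 21.1 makes the eye the unit of analysis. All implanted eyes "will be pooled together for analysis; which include both study eyes from bilaterally implanted subjects and one study eye from unilaterally implanted subjects". Under section 21.2 the primary proportion "will be reported along with the 95% confidence interval for this proportion", again with no method named. The success rule there is: "The clinical success criterion will be that 90% of eyes will have lens rotation of 5 degrees or less at 1-week".

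**The concern.** Two eyes of one person share anatomy, surgeon and site, so their rotation outcomes may be positively correlated. If they are, 200 eyes that include 75 pairs carry less information than 200 eyes from 200 people. Section 21 contains no design effect, clustered variance or one-eye-per-subject analysis. The 308 eyes that may be enrolled are not a hidden allowance, because the evaluable target and the precision statement are both set at 200 and the stated reasons for the margin do not include correlation.

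Precision is the only argument given for the sample size, and this interval is the only measure of uncertainty planned for the primary endpoint. At stake are a stated precision that is too favourable and a reported 95% interval that may cover less often than 95%.

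**Working it through.** **Inputs.** n = 200 eyes, two-sided 95% (z = 1.96) and p = 0.95 or higher (section 21.5). 75% of eyes from bilateral subjects (Synopsis, sections 8 and 10.1), so 150 eyes in 75 pairs plus 50 single eyes, or 125 subjects. The fellow-eye correlation rho is not in the documents. It is an assumption here, shown at 0.1, 0.3 and 0.5.

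**1. Reproduce the plan's figure.** Wald, independent eyes: 1.96 × √(0.95 × 0.05 / 200) = 3.02 points, which rounds to 3.0. Exactly 3.0 would need 1.96² × 0.0475 / 0.03² = 202.7, so 203 eyes. Other forms at 190/200 do not give 3.0:

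| Method, independent eyes | Points below | Points above |
|---|---|---|
| Wald | 3.02 | 3.02 |
| Wald, continuity-corrected | 3.27 | 3.27 |
| Wilson | 3.96 | 2.26 |
| Exact (Clopper-Pearson) | 4.00 | 2.58 |

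The exact lower arm is still 3.04 at 196/200 and first falls below 3.0 at 197/200 (2.82). Wilson gives 3.03 and 2.82.

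**2. Allow for pairs.** With m pairs among n eyes, Var = p(1−p)/n² × (n + 2·m·rho), so the design effect is 1 + (2m/n)·rho. At 75 pairs it is 1 + 0.75·rho. Wald half-width at 95%:

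| rho | Design effect | Effective eyes | Half-width |
|---|---|---|---|
| 0 | 1.000 | 200 | 3.02 |
| 0.1 | 1.075 | 186 | 3.13 |
| 0.3 | 1.225 | 163 | 3.34 |
| 0.5 | 1.375 | 145 | 3.54 |

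Any rho above about 0.026 takes the half-width past 3.05.

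**3. Vary the mix.** The 75/25 split is a target, not a limit. With 116 bilateral subjects allowed, 200 evaluable eyes could be 100 pairs. If all loss from 2 × 116 + 76 = 308 eyes to 200 were random and eye by eye, about 116 × (200/308)² = 49 pairs would remain complete. For rho 0.1, 0.3 and 0.5 the half-widths are 3.09, 3.23 and 3.37 with 49 pairs, and 3.17, 3.44 and 3.70 with 100.

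**4. Where 3.0 still holds.** Largest rho = [(0.03/1.96)² × 200 / (p(1−p)) − 1] / (2m/n). At 75 pairs this is below 0 at p = 0.95, 0.12 at 0.955, 0.29 at 0.96, 0.52 at 0.965, 0.81 at 0.97 and above 1 at 0.975.

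**5. Coverage of a nominal 95% interval.** Exact enumeration at p = 0.95, 75 pairs plus 50 singles:

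| Interval | rho 0 | 0.1 | 0.3 | 0.5 |
|---|---|---|---|---|
| Wald, pairing ignored | 92.6% | 91.6% | 89.5% | 87.5% |
| Exact, pairing ignored | 96.7% | 96.1% | 94.7% | 93.3% |
| Robust Wald, clustered by subject | 93.0% | 92.7% | 92.3% | 92.2% |
| Logit scale, clustered by subject | 95.6% | 95.7% | 95.5% | 95.3% |

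The Wald shortfall at rho 0 comes from the approximation, not from pairing. The exact interval drops below 95% only from rho of about 0.26 (about 0.19 with 100 pairs, 0.4 with 49).

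**6. Precision of the proposed interval.** Logit scale at an observed 95%, with limits from logit(0.95) ± 1.96 / √(n_eff × 0.95 × 0.05), back-transformed, at 75 pairs: 4.24, 4.62 and 4.99 points below and 2.35, 2.46 and 2.56 above for rho 0.1, 0.3 and 0.5. With independent eyes it is 4.04 below and 2.29 above.

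**The case against.** The sum in section 21.5 is correct; the fault lies in what it leaves unsaid. The size of the shortfall depends on a correlation that the documents do not give: at 0.1 the half-width moves only from 3.02 to 3.13. The statement covers 95% or higher, and the problem sits at and just above 95%. No decision turns on it: this is a single-arm study of a marketed lens, the 90% criterion is not tied to an interval limit, and at an observed 95% even rho = 1 leaves the Wald lower limit at 91.0%. If the sponsor intends an exact interval, ignoring pairing does no harm to coverage at low correlation.

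All of this stands, and it limits the weight of the point. It does not remove it. Treating the eyes as independent is itself an assumption, rho = 0, and the plan does not state it. The defence from the exact interval also undercuts section 21.5, because that interval does not have a 3.0-point lower arm at 95%.

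One further caution is fair. Against the published 3.0, the larger step is the interval method (about 1.0 point, from 3.02 to 4.04 on the logit scale); correlation adds 0.2 to 0.95 points (4.24 − 4.04 to 4.99 − 4.04). The restated text should keep the two apart.

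**Conclusion.** The concern holds and should be fixed. The 3.0 points describe the planned interval at 95% only if it is an uncorrected Wald interval on independent eyes, which the targeted mix of pairs and single eyes does not supply if fellow eyes are positively correlated. At the target mix the Wald half-width is 3.13 to 3.54 points for assumed correlations of 0.1 to 0.5. Coverage with pairing ignored is then 91.6 to 87.5% for Wald and 96.1 to 93.3% for the exact interval. The omission is certain; its size is conditional on the assumed correlation and on the number of complete pairs. The finding that needs no assumed correlation is the 4.0-point lower arm of an exact or Wilson interval at 190/200. Neither the pooled proportion nor the success verdict changes.

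**What to change.** In section 21.2, add text such as:

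> The two-sided 95% CI will treat the subject as the cluster (intercept-only GEE, logit link, independence working correlation so that the estimate stays the pooled proportion of eyes, robust variance, back-transformed). If every eye is a success, an exact interval on the number of subjects will be used.

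With 125 subjects, the all-success lower limit is 0.025^(1/125) = 97.1%. A Wald interval on the proportion scale should be avoided even with robust variance, since it covers only about 92 to 93% at p = 0.95.

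In section 21.5, restate the precision for the same interval:

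> With 200 evaluable eyes at the target mix (75 pairs plus 50 single eyes) and an observed proportion of 95%, the lower limit lies about 4.2, 4.6 or 5.0 points below, and the upper limit about 2.4 to 2.6 points above, for an assumed fellow-eye correlation of 0.1, 0.3 or 0.5 (4.0 below and 2.3 above with independent eyes).

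Label the correlation as an assumption, and replace the range if the sponsor has its own fellow-eye estimate. Another subject-clustered, non-Wald interval would serve if section 21.5 is restated for it; Wilson on the effective number of eyes gives about 4.1, 4.5 and 4.8 points below.

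The cost is two or three sentences and a few lines of code. The stated precision looks less favourable, and the logit interval is slightly conservative in most cases (coverage 94.9 to 97.0% over 49 to 100 pairs, p of 0.95 and 0.97, rho 0 to 0.5). No extra eyes are needed. Restoring a 3.0-point Wald half-width at 95% would take 218, 249 or 279 evaluable eyes for rho 0.1, 0.3 or 0.5 (202.7 × the design effect, rounded up), and nothing in the plan depends on that exact figure.
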